### 5.1.1 Impact of COVID-19

A listing of all visits affected by COVID-19 will be presented based on the Enrolled Set including the visit, date of visit, relationship to COVID-19, impact category and a narrative (short description) of the event. This data will be summarized by treatment group at completion of PA0008, and overall for the ES for the following:

- Impact of COVID-19 for any reason
- Impact of COVID-19 for any reason by country

In addition, in order to assess the potential impact of COVID-19 on the collection and reporting of efficacy data a separate listing and summary will be presented to display missing data and data collected via an alternative modality (eg, phone, video call). For the purpose of these displays, missing data will be presented only for visits affected by COVID-19 (as reported on the dedicated eCRF page) ie, missing data at other visits and for other reasons will not be included.

The following efficacy assessments may be collected remotely:

- HADS
- HAQ-DI
- SF-36
- PGADA
- PtAAP
- PsAID-9

For visits conducted remotely (as reported on the dedicated eCRF page), it is not possible to assess MASES, PhGADA, BSA, PASI, LDI, TJC or SJC, and therefore these assessments will be missing at the specified visit. In addition, for any missed visit or a visit conducted remotely, the CRP assessment will also be missing. Such assessments will be considered to be missing as a result of COVID-19. For these visits, it will therefore not be possible to assess DAS28(CRP) and may not be possible to classify the subject as an ACR responder or nonresponder.

A listing will be presented showing each impacted visit based on the FAS. This will include the planned visit, the visit date, and details of the assessments conducted remotely and/or those missing as a result of COVID-19.

These data will be presented in a summary table by treatment group at completion of PA0008 and overall for the FAS.

For both the listing and the summary table, only visits at which efficacy assessments are scheduled will be included.

## 5.2 Protocol deviations

The number and percentage of subjects with an important protocol deviation and with each category of important protocol deviation (as described in [Section 3.4](#)) will be presented by treatment group at completion of PA0008 and overall for the ES.

Important protocol deviations, including deviation type and description, will be listed for the ES.

A separate listing of COVID-19 related important protocol deviations will be presented, based on the ES. COVID-19 related important deviations will be identified by the prefix of 'COVID' in the deviation verbatim text.

## 6 DEMOGRAPHICS AND OTHER BASELINE CHARACTERISTICS

### 6.1 Demographics

Demographic variables (age [at time of informed consent], gender, racial group, ethnicity, weight, height, body mass index [BMI], country, and geographic region) will be summarized by treatment group at completion of PA0008 and overall for the SS.

One summary table will be produced for PA0008 Baseline values. Age, sex, weight and BMI will be collected at EV or recalculated in PA0009 and will be listed only.

Age and BMI will be summarized as continuous and as categorical variables:

Age will be categorized as:

- $\leq 18$ , 19 to  $< 65$ ,  $\geq 65$  years (clinicaltrials.gov requirement).
- 18- $< 65$ , 65 to  $< 85$ ,  $\geq 85$  years (EudraCT requirement).
- 18 to  $< 45$ ,  $\geq 45$  to  $< 65$ ,  $\geq 65$  years (bimekizumab program conventions).

BMI ( $\text{kg}/\text{m}^2$ ) is calculated based on the height (in m) and the weight (in kg) using the formula:

$$BMI = \frac{\text{weight}}{\text{height}^2} \quad (8)$$

Even if available in the database, BMI will be re-calculated. BMI is rounded to 1 decimal place. BMI will be categorized as follows:  $< 25$ , 25 to  $< 30$ ,  $\geq 30$   $\text{kg}/\text{m}^2$ .

Demographic data, including PA0008 Baseline and PA0009 EV values for the repeated variables, will be listed for the ES.

### 6.2 Other baseline characteristics

PsA history (date of first diagnosis, time since first diagnosis of PsA [at time of enrolment in PA0008 and at time of enrolment in PA0009], age at first diagnosis date, and PsA subtype [polyarticular – symmetric arthritis, oligoarticular – asymmetric arthritis, distal interphalangeal, joint predominant, spondylitis predominant, arthritis mutilans]) will be summarized by treatment group at completion of PA0008 and overall for the SS.

Time since first diagnosis of PsA will be summarized as a continuous variable and as a categorical variable. Time since first diagnosis of PsA at time of enrolment in PA0008 will be taken from the PA0008 database. Time since first diagnosis of PsA at time of enrolment in PA0009 will be calculated as below, where date of diagnosis will be taken from the PA0008 database:

$$\begin{aligned} \text{Time since first diagnosis} \\ &= \text{date of informed consent in PA0009} \\ &- \text{date of first diagnosis in PA0008} \end{aligned} \quad (9)$$

Time since first diagnosis for each study will be categorized as:  $< 2$ ,  $\geq 2$  years.

Age at first diagnosis will be taken from the PA0008 database.

PsA history will be listed for the ES.

The following Baseline characteristics will be summarized by treatment group at completion of PA0008 and overall for the SS:

- TJC.
- SJC.
- CRP.
- Rheumatoid factor (Positive, Negative).
- Anti-cyclic citrullinated peptide (CCP) antibodies (Positive, Negative).
- NSAID therapy prior to first dose in PA0008 (yes, no). The value in the PA0008 database for past NSAID therapy (as collected on the eCRF) will be used for PA0009, without additional derivation.
- Anti-TNF therapy prior to first dose in PA0008 (yes, no). The value in the PA0008 database for past anti-TNF therapy (as collected on the eCRF) will be used for PA0009, without additional derivation.
- Psoriasis BSA category (<3%, ≥3% to <10%, ≥10%).
- Nail psoriasis (yes, no).
- Dactylitis (yes, no).
- Enthesitis (yes, no).
- Current number of NSAID therapies (0, 1, 2, ≥3).
- Current synthetic DMARDs (methotrexate [MTX], sulfasalazine, hydroxychloroquine) (yes, no).

One summary table will be produced for PA0008 Baseline values and another for PA0009 EV values. Rheumatoid factor, anti-CCP antibodies, nail psoriasis, dactylitis and NSAID and anti-TNF therapy prior to first dose in PA0008 will be based on data collected in PA0008 and will be included in the PA0008 Baseline table only.

TJC, SJC, CRP, psoriasis BSA and current NSAID and synthetic DMARD therapy will be included in both tables. CRP values at PA0009 EV will be taken from the Week 48 record in the PA0008 database. For the summary of PA0009 EV data, current NSAID and synthetic DMARD therapy are defined as medications that are ongoing at the PA0009 EV, or that started on the date of the PA0009 EV. This does not include medications that were stopped on the date of the PA0009 EV.

Baseline characteristics, including PA0008 Baseline and PA0009 EV values for the repeated variables, will be listed for the ES.

### **6.3 Medical history and concomitant diseases**

Medical history and ongoing medical conditions collected prior to the start date of study medication in PA0008 and any additional conditions collected prior to the start date of study medication in PA0009 will be summarized together. The number and percentage of subjects

with any condition, and with each condition in each MedDRA SOC and PT, will be presented by treatment group at completion of PA0008 and overall, for the SS.

Medical history and ongoing medical conditions, including the start date and end date (or ongoing if applicable), will be listed for the SS. The listing will indicate whether the condition was reported in PA0009.

A glossary of all medical history conditions including the reported term, PT, and SOC will also be presented.

The number and percentage of subjects with a history of each category of extra-articular manifestations (uveitis, inflammatory bowel disease [IBD], psoriasis, peripheral arthritis, enthesitis, dactylitis) will be summarized by treatment group at completion of PA0008 and overall, for the SS, based on data collected at the PA0009 EV. The number and percentage of subjects with an occurrence of extra-articular manifestations (uveitis, IBD) post-PA0009 EV will be summarized by treatment group at completion of PA0008 and overall, for the SS. Extra-articular assessments will be listed for the SS.

#### **6.4 Past, prior and concomitant medications**

Only medications that were ongoing at the end of PA0008 or were started during PA0009 will be reported.

Concomitant medications are medications taken on at least 1 day in common with the dosing period of PA0009 (as defined in [Section 3.2.2](#)). A medication is classed as concomitant if the start date is no later than the end date of study medication in PA0009 + 28 days, and the stop date is either missing or on or after the start date of study medication in PA0009. This includes medications that started prior to dosing in PA0009 and continued after.

For the purposes of the analysis, past medications are medications that started and stopped prior to dosing in PA0008. This includes past TNF therapy as used for subgroup analyses, MI modelling and Baseline characteristics and past NSAID therapy (for Baseline characteristics).

Missing or partial medication start and stop dates will be imputed as described in [Section 4.2.3](#). Imputations will be performed before calculation of relative study days and classification as concomitant.

The number and percentage of subjects taking concomitant medications will be summarized by anatomical therapeutic chemical (ATC) class, presenting Anatomical Main Group (ATC Level 1), Pharmacological Subgroup (ATC level 3), and PT in separate tables for PsA concomitant medications and other concomitant medications, by treatment group at completion of PA0008, and overall for the SS. The complete list of PsA concomitant medications is included in the protocol [Section 7.8.1](#) and includes: NSAIDs, corticosteroids, DMARDs, (MTX, sulfasalazine, leflunomide and apremilast), and joint injections.

PsA concomitant medications will be identified following the procedure outlined in [Section 6.5](#).

All medications reported in PA0009, including flags to identify concomitant, PsA and rescue medications, start and stop days relative to the start date of study medication in PA0008, and start and stop days relative to the start of study medication in PA0009, will be listed for the ES.

A glossary of all medications including the Anatomical Main Group (ATC Level 1), Pharmacological Subgroup (ATC level 3) PT and reported term will also be presented, based on the ES.

## 6.5 Prohibited medication and rescue therapy

The following medication categories will be identified:

- Rescue medications as defined below. Subjects in the category ‘Any concomitant rescue therapy in PA0009’ will be considered SS Sub-population 2 and other subjects will be considered SS Sub-population 1. Rescue medications will be identified in the study database using the flag collected in the eCRF.
- DMARDs to identify subgroups/covariates.
- PsA medications as defined in the protocol Section 7.8.1 (this includes DMARDs).
- Prohibited medications.

Rescue medication, DMARDs, and PsA medications will be classified into subcategories for reporting purposes. These will be reviewed and confirmed by the study physician in order to ensure that the classifications are correct.

The number and percentage of subjects who receive the following categories of rescue medication will be summarized by treatment group at completion of PA0008 and overall for the SS.

- Any rescue medication in PA0009 that is classified as a concomitant medication as defined in [Section 6.4](#).
- NSAID at PA0009 EV.
- No NSAID at PA0009 EV.
  - No NSAID at PA0009 EV and initiate NSAID [but not Cox-2 inhibitors] in PA0009 (only the initiation of NSAIDs that are classified as concomitant medications as defined in [Section 6.4](#) will be included).
  - No NSAID at PA0009 EV and initiate Cox-2 inhibitors in PA0009 (only the initiation of Cox-2 inhibitors that are classified as concomitant medications as defined in [Section 6.4](#) will be included).
- Use of MTX, sulfasalazine, leflunomide, apremilast or DMARD combinations in PA0009 (with the exception of MTX and leflunomide together). Only concomitant medications will be included as defined in [Section 6.4](#). For the programming of combination medications the following rules will be applied:
  - If any combination of DMARDs is taken at least once during the study the subject will be counted in the ‘combination of DMARDs’ main category

- If LEF and MTX are taken in combination (with or without another DMARD) at least once during the study the subject will be counted in the ‘combination of LEF and MTX’ subcategory
- If LEF is taken in combination with another DMARD (not MTX) at least once during the study the subject will be counted in the ‘combination of DMARDs (except LEF and MTX together)’ subcategory
- If MTX is taken in combination with another DMARD (not LEF) at least once during the study the subject will be counted in the ‘combination of DMARDs (except LEF and MTX together)’ subcategory
- If any other combination of DMARDs is taken (not including LEF or MTX) at least once during the study the subject will be counted in the ‘combination of DMARDs (except LEF and MTX together)’ subcategory
- For all the above, medications taken in combination will be defined as those with at least one concomitant study day in common (after imputation of partial dates as described in [Section 4.2.4](#)) and both classified as concomitant medications
- If more than 1 DMARD medication is taken but the dates are not overlapping, these will be counted in both the relevant individual categories in the table only (eg, LEF and MTX individual categories)

Subjects will be counted in all applicable categories and subcategories in the table ie, if a subject receives both LEF and apremilast and these have at least 1 study day in common, these will be counted in both the combination rows and the individual medication rows. Subjects will be counted only once in each category.

- Intra-articular corticosteroid in PA0009 that is classified as a concomitant medication as defined in [Section 6.4](#).
- Oral corticosteroid in PA0009 that is classified as a concomitant medication as defined in [Section 6.4](#).
- Analgesics in PA0009 that are classified as concomitant as defined in [Section 6.4](#).

Rescue therapy category and medication name, start date, and day relative to start of study medication in PA0008 and PA0009 will be listed for the SS.

PRN analgesic and PRN opioid analgesic use within 24 hours prior to study visits will be listed for the ES, based on the dedicated eCRF page for prohibited medications.

## 6.6 Concomitant medical procedures and procedure history

A listing of concomitant medical procedures and a separate listing of procedure history will be presented for the ES.

## 7 MEASUREMENTS OF TREATMENT COMPLIANCE

Compliance will be summarized using the number of doses received relative to the number of doses expected:

$$\text{Percent treatment compliance} = 100 * \frac{\text{Number of doses received}}{\text{Number of doses expected}} \quad (10)$$

where the total number of expected doses is derived relative to when the subject finishes treatment. If a subject completes treatment 26 doses are expected (EV and every fourth week afterwards until PA0009 Week 100). If a subject discontinues early, then the number of expected doses is based on the time of study discontinuation relative to the planned dosing visits (taking into account the permitted visit window). If the date of study discontinuation is missing the final contact date (as reported on the eCRF) will be used instead.

A summary of percent treatment compliance, both continuous and categorized as  $\leq 75\%$  and  $>75\%$ , will be provided by treatment group at completion of PA0008 and overall for the SS.

Treatment compliance will be listed for the SS. A separate listing of study medication administration (including injection dates and times, kit numbers, who performed the injection and the location of the injection) will be presented.

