6.3 Withdrawal criteria

Subjects are free to withdraw from the study at any time, without prejudice to their continued care.

Subjects should be withdrawn from the study and will be asked to complete the Early Termination (ET) Visit and SFU Visit (20 weeks after the last received dose) if any of the following events occur:

1. Subject withdraws his/her consent.
2. There is confirmation of a pregnancy in a female subject during the study, as evidenced by a positive pregnancy test.
3. The Sponsor or a regulatory agency requests withdrawal of the subject.
4. Subject develops an illness that in the opinion of the Investigator would interfere with his/her continued participation, if the risk of continuing participation outweighs the potential benefit.
5. Subject develops erythrodermic, guttate, or generalized pustular form of PSO.
6. Subjects considered to have either a suspected new latent tuberculosis (LTB) infection or who develops an active tuberculosis (TB) or nontuberculosis mycobacterium infection during the study (including but not limited to, conversion demonstrated by interferon-gamma release assay (IGRA) or other diagnostic means) must be immediately discontinued from study medication and an unscheduled visit must be conducted as soon as possible, but not later than the next regular visit.

The subject must be permanently withdrawn if further examinations result in a diagnosis of active TB, or if the subject is diagnosed with LTB infection with no initiation of prophylactic treatment, prematurely discontinues prophylactic treatment, or, in the opinion of the Investigator or Sponsor, is noncompliant with prophylactic TB therapy.

Confirmed active TB is an SAE and must be captured on an SAE Report form and provided to the Sponsor in accordance with SAE reporting requirements. As with all SAEs, periodic follow-up reports should be completed as per protocol requirements until such time as the TB infection resolves.

7. Subject is noncompliant with the study procedures or medications that may present a risk to the safety of the subject in the opinion of the Investigator.
8. Subject uses prohibited concomitant medications as defined in [Section 7.8.2](#) that may present a risk to the safety of the subject in the opinion of the Investigator and/or the Medical Monitor.

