Investigators should attempt to obtain information on subjects in the case of IMP discontinuation to complete the final evaluation. Subjects with PDILI should not be withdrawn from the study until investigation and monitoring are complete. All results of these evaluations and observations, as well as the reason(s) for IMP discontinuation and subject withdrawal (if applicable), must be recorded in the source documents. The CRF must document the primary reason for IMP discontinuation.

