7.8.2 Prohibited concomitant treatments (medications and therapies)

Prohibited and/or restricted medications are summarized in [Table 7-1](#) and [Table 7-2](#).

Table 7-1: Prohibited or restricted medications

Drug class	Dose	Comments
Analgesics, including opioid analgesics (acetaminophen/paracetamol, etc)	Any dose	Any ad hoc use in the 24 hours prior to any study visit is prohibited. Stable doses of analgesics (including opioids) permitted.
TNF inhibitor: -infliximab -adalimumab -etanercept -golimumab -certolizumab pegol	Any dose	This applies to biosimilar versions of any TNF inhibitors.
Any non-TNF biologic medications	Any dose	Any exposure history is prohibited.
All other DMARDs	Any dose	Only permitted medications as per Section 7.8.1 .

DMARD=disease-modifying antirheumatic drug; TNF=tumor necrosis factor

Table 7-2: Additional prohibited psoriasis treatments

Drug class
Phototherapy
High potency topical steroid, vitamin D analogues, topical retinoids, keratolytics, coal tar, fumaric acid esters use except as detailed in Section 7.8.1
Systemic retinoids

Subjects who take prohibited medications may be withdrawn from study treatment but followed until the SFU Visit. The decision to withdraw a subject for taking prohibited medications should be made in consultation with the Medical Monitor.

Vaccines

Administration of live, attenuated vaccines is not allowed during the conduct of the study or for 20 weeks after the last dose of study drug. Administration of non-live, inactivated vaccines is allowed during the study at the discretion of the Investigator.

Live vaccinations include, but are not limited to, the following: anthrax vaccine, intranasal influenza vaccine, measles-mumps-rubella vaccine, polio live oral vaccine, smallpox vaccine, TB Bacillus Calmette-Guérin vaccine, typhoid live oral vaccine, varicella vaccine, and yellow fever vaccine.

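### SAP Section 7 counts expected doses for early discontinuers to study discontinuation or final contact, so compliance is understated when that date falls after treatment has permanently stopped and further dosing visits have passed

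*SAP*

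**What the plan says.** SAP Section 7 defines compliance as doses received over doses expected, as a percentage. Its general rule is that "the total number of expected doses is derived relative to when the subject finishes treatment". For a treatment completer, "26 doses are expected (EV and every fourth week afterwards until PA0009 Week 100". For an early discontinuer, "the number of expected doses is based on the time of study discontinuation relative to the planned dosing visits", allowing for the visit window. It adds: "If the date of study discontinuation is missing the final contact date (as reported on the eCRF) will be used instead". The section plans "A summary of percent treatment compliance, both continuous and categorized as" at most 75% or above 75%, so exactly 75% falls in the low category.

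The protocol separates the end of treatment from the end of participation in several places:

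- Section 6.3: subjects who are withdrawn "will be asked to complete the Early Termination (ET) Visit and SFU Visit (20 weeks after the last received dose").
- Section 7.8.2: "Subjects who take prohibited medications may be withdrawn from study treatment but followed until the SFU Visit".
- Section 6.3.1, on potential drug-induced liver injury (PDILI): "Subjects with PDILI should not be withdrawn from the study until investigation and monitoring are complete".
- Sections 9.6.5 and 9.6.5.3: after active tuberculosis, study medication stops at once, but the Early Termination (ET) visit may take place as late as the next scheduled visit.

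**The concern.** The general rule and the early-discontinuer rule in SAP Section 7 use different end points, and the SAP treats them as different dates elsewhere. Section 3.2.2 ends the Treatment Period with study medication and starts the SFU Period the next day. Section 5.1 draws study termination and study-medication discontinuation from separate eCRF pages. No rule stops the count of expected doses once treatment has permanently stopped.

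A subject taken off study medication as the protocol requires, and then followed, can therefore be scored as if doses had been skipped. The category of 75% or less would then mix stopping treatment with missing injections, which are different things to a reader of a compliance table. Because the SAP does not say which visit dates study discontinuation, two programmers could also obtain different counts from the same data.

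**Working it through.** **The plan's own figure.** One dose at entry and one every 4 weeks to Week 100 gives 100/4 + 1 = 26, which matches SAP Section 7.

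**Inputs.** Dosing every 4 weeks (Protocol 7.2); visit window of ±7 days, and SFU at 20 weeks after the last dose with a window of −3/+7 days (Protocol Table 5-1); cut-off of at most 75% (SAP 7).

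**Formula.** Take a subject who received n doses and missed none, so the last dose was at Week 4(n − 1). Let k be the number of planned dosing visits counted between the last dose and the date used.

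compliance = 100 × n / min(26, n + k)

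Below the cap of 26, compliance is at most 75% when n ≤ 3k. The latest last dose that qualifies is then Week 4(3k − 1) = 12k − 4. The cap does not alter these thresholds: with k = 5 it first applies at n = 22, where 22/26 = 84.6%.

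| Extra planned doses k | Largest n at ≤75% | Compliance | Week of last dose |
|---|---|---|---|
| 0 | none | 100% | never |
| 1 | 3 | 3/4 = 75.0% | 8 |
| 2 | 6 | 6/8 = 75.0% | 20 |
| 3 | 9 | 9/12 = 75.0% | 32 |
| 4 | 12 | 12/16 = 75.0% | 44 |
| 5 | 15 | 15/20 = 75.0% | 56 |

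One dose more moves the subject out of the low category: 13/17 = 76.5% with k = 4, and 16/21 = 76.2% with k = 5. Earlier stops score lower. With k = 5, a last dose at Week 20 gives 6/11 = 54.5%, and one at Week 8 gives 3/8 = 37.5%.

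**How large k can be.** A 20-week gap is 140 days, with planned doses at days 28, 56, 84, 112 and 140. All five count if a visit counts once its window opens or its nominal day arrives. Four count if a visit counts only once its +7-day window has closed, because that falls on day 147. Across all permitted deviations of the last dose and the SFU visit, k is 4 or 5 under each of these three readings.

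**A late ET visit.** Take a last dose at Week 12 (n = 4) and an ET visit at Week 24, assuming that the next scheduled visit means the next site visit. Weeks 16 and 20 are then counted, and Week 24 as well if that visit is treated as due. Compliance is 4/6 = 66.7% or 4/7 = 57.1%.

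**The case against.** The strongest reply is that study discontinuation is probably dated at or near the ET visit, not at SFU. Protocol Section 8.10 has early withdrawers undergo the Week 104 assessments and then enter the SFU Period. SAP Section 5.1 defines study completion by attendance at Week 104, not SFU, and lists the premature discontinuation date and the final contact date as separate items. Footnote b of SAP Table 10-2 likewise lists the last visit, SFU included, separately from study termination. This carries weight. A reader might infer that every early discontinuer gains four or five undue doses, and that all fully compliant subjects stopping by Week 56 are misclassified. The documents do not support that. The long gap needs a date at about SFU, and the text leans the other way without settling it.

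The reply does not remove the problem. It does not cover subjects off treatment but still followed under Protocol Sections 7.8.2 and 6.3.1, nor the final-contact fallback. Nor does dating at ET guarantee no effect, since a late ET visit can add one to three planned doses.

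A second reply is that stopping the count at the last dose would hide injections skipped just before withdrawal. That is correct, and it determines which date the fix should use.

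A third is that little depends on the result. There is no per-protocol set, and no primary or secondary variable uses this percentage. SAP Sections 5.1 and 7 also provide for medication discontinuation with reasons and individual injection dates, so a reader can separate stopping from skipping. This stands, and it keeps the point minor.

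**Conclusion.** The early-discontinuer rule is inconsistent with the section's own opening rule. As written, it understates compliance for any subject whose recorded date of study discontinuation or final contact comes after treatment has permanently stopped and at least one further planned dosing visit has been counted. The effect ranges from nothing, when the date precedes the next due dose, to the k = 5 row of the table, which is an upper bound. That bound assumes no missed dose, a date at about SFU and all five intervening visits counted; with four counted, the limit is Week 44. The documents do not say how many subjects would be affected or which date the eCRF records. As far as they show, the impact is confined to the descriptive compliance summary and listing.

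**What to change.** For subjects who stop early, count planned dosing visits, with the visit window, up to the date study medication was permanently discontinued. If that date is missing, use the treatment end date under SAP Section 4.2.5 in place of final contact. Also state whether a planned visit counts when its window opens, on its nominal day or when its window closes.

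Doses skipped before the decision to stop then still count. For example, with a last dose at Week 12, Weeks 16 and 20 skipped and treatment stopped at Week 22, compliance is 4/6 = 66.7%. A subject who missed nothing and stopped before the next dose was due scores n/n = 100%.

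The cost is a small change to the SAP wording and a small programming change. SAP Section 5.1 already refers to a study-medication discontinuation page, but the documents do not say that it records a date, so this should be checked first. One small downside remains: where only the last-dose date is available, doses skipped just before stopping go uncounted, and the example above would score 4/4 = 100%.
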